## Research Protocol/Protocol Addendum Template

---

Adverse events will be reported with continuing review. Information security or privacy incidents will be reported to the ISSO or PO within one hour of discovery. As described above, we consider that the following events are anticipated adverse events: suicidal ideation, suicide attempts, suicide, hospitalizations or emergency room for worsening psychiatric symptoms or suicidal behavior, drug or alcohol relapse or admission to a detox facility, or imprisonment.

### **Reasons for stopping assigned treatment and follow-up:**

We will consider that the following events are reasons to stop assigned treatment and or follow-up of an enrolled patient: (1) death because the patient would no longer be accessible to study staff; or (2) patient requests to withdraw from the study. In the event that the patient is assigned to the intervention, we will ask the patient if they are willing to continue with the outcome assessments but respect his/her wishes if he/she chooses to withdraw entirely from the study.

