### **Project Proposal, Phase 3, Aim 3**

To test our hypotheses as described above, we propose to conduct an assessor - blinded RCT comparing the BESST intervention plus standard care to standard care alone. We will enroll up to 25 patients who are 18 years or older and are being discharged from a VA-CCN mental health treatment setting. The primary aim is to determine whether the BESST intervention reduces suicidal ideation at one and three months after discharge. The secondary aim is to evaluate the impact of the BESST intervention on other related measures of suicide risk including hopelessness, social connectedness, fatal/non-fatal suicide attempts and treatment engagement.

**Randomization:** Prior to the start of study enrollment, the study team otherwise not involved in recruitment will independently prepare allocation cards using a permuted block schedule. The same study staff member will then put these prepared allocation cards into sealed, opaque, numbered envelopes. After obtaining consent and completing the baseline assessment (see description below), the study staff member will take the next numbered envelope from the box (described above) and open the envelope to determine the patient's assignment. In the event that the patient has been assigned to the intervention, the study staff will notify the intervention staff in order that the intervention staff can initiate the intervention. Otherwise, the patient will be informed that they have been assigned to usual care.

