**Regular Contact:** The patients will maintain regular contact with the intervention staff member for a total of seven contacts over the course of the three months after discharge. At each of these contacts, the intervention staff member will monitor the patient's symptoms, assess treatment adherence, review the safety plan with the patient, and, if necessary, assist the patient with engaging in care. The contacts are designed to be highly interactive, allowing time for questions and providing patients with written materials that they can keep for future reference. Depending on the patient's preference, the regular contacts will be delivered over the phone (or VA Video Connect) or in-person in a private office on the grounds of the WRJ VAMC. These visits last roughly 15-30 minutes.

**Standard Care:** Regardless of study assignment, all patients will have access to standard care. This includes recommendations for mental health follow-up as deemed appropriate by the discharging treatment team. Patients may also be offered specific treatments to address their mental health symptoms after discharge. It is also conceivable that a patient may be on the High Risk for Suicide List. Patients on the High Risk for Suicide List receive enhanced oversight as

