## Research Protocol/Protocol Addendum Template

behaviors. The scale asks the assessor to document the actual and potential lethality of these behaviors. The C-SSRS is widely used in the VA.

**Secondary Outcome (Substance use):** We will assess substance use at baseline and follow-up assessments using a timeline follow-back approach. This method is commonly used in research studies to assess substance use patterns.

**Study Design:** As shown in **Figure 3** below, patients allocated to the BESST intervention will meet with the intervention staff around the time of discharge. During this visit, the patients will receive a brief educational intervention. Depending on patient preference, this visit will occur over the phone (or VA Video Connect). Depending on patient preference, the regular contacts will occur in a private office on the WRJ VAMC campus, or the contacts will occur over the phone (or VA Video Connect).

**Figure 3.** Schedule of Assessments and Interventions.

BIC= VA Brief Intervention and Contact Program; D/C = discharge; dy = days; m = months; MH = Mental Health; T0, T1, T2 = assessment time points; wk = weeks

All patients (including patients randomized to the intervention) will have access to standard care. Furthermore, regardless of study assignment, all patients will undergo outcome assessment at baseline (0M), one month (1M), and three months (3M). These assessments will be conducted by the independent outcome assessor. We anticipate that, in most cases, the baseline assessment will occur around the time of discharge. However, because patients will be recruited remotely, we anticipate that the baseline assessments may in some cases happen a few weeks after discharge. Depending on patient preference, the independent outcome assessor will conduct the follow-up assessments in a private office on the WRJ VAMC campus, over the phone, or using VA Video Connect. The assessors will be blinded to study assignment and the patients will be instructed to not reveal their status to the assessor.

Because we are recruiting patients from a large geographic area (New Hampshire, Maine and Vermont), we anticipate that several enrolled patients will prefer phone (or VA Video Connect) over in-person follow-up. Fortunately, the assessment instruments that we selected for this study can be administered over the phone or in person.

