**Statistical Analyses:** We will conduct the analysis based on the intention-to-treat principle. Below, we have outlined the specific analysis plan for assessing each of the primary and

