### ***Therapeutic Risks***

During the study, the research staff will ask patients questions about how they are feeling and their interactions with other people. Patients will be exposed to these therapeutic risks during the baseline and each follow-up assessment. In addition, patients who receive the intervention condition will also be exposed to these therapeutic risks at the intervention visits (brief education visit plus seven contact visits after discharge). In some cases, patients can feel embarrassed, nervous, bored, or generally uncomfortable when they are asked to answer these types of questions. However, because we have sufficient safeguards in place to mitigate these potential risks, we believe that the overall therapeutic risk from this study to enrolled patients is very low.

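### The request to continue outcome assessments after withdrawal is written for the intervention arm only, so the effort to keep outcome data depends on arm

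*Combined protocol and SAP*

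**What the plan says.** All references are to the combined protocol and SAP.

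- **Reasons for stopping assigned treatment and follow-up.** There are two triggers for any enrolled patient: death, or "patient requests to withdraw from the study". The next sentence applies to one arm only, namely if "the patient is assigned to the intervention, we will ask the patient if they are willing to continue with the outcome assessments". Staff will also "respect his/her wishes if he/she chooses to withdraw entirely from the study". Nothing is stated for a usual-care patient who asks to withdraw.
- **Randomization.** Patients learn their arm after baseline. For those not given the intervention: "Otherwise, the patient will be informed that they have been assigned to usual care". Study Population and Recruitment confirms that patients cannot be blinded, while the outcome assessor is.
- **Statistical Analyses.** "We will conduct the analysis based on the intention-to-treat principle". Missing data are to be handled by maximum likelihood within a mixed model. No sensitivity analysis is given.
- **Therapeutic Risks and Standard Care.** The intervention arm receives a "brief education visit plus seven contact visits after discharge". For usual care, "Regardless of study assignment, all patients will have access to standard care". The assessments at 0, 1 and 3 months apply to both arms (Study Design).

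**The concern.** The same event, a request to leave the study, leads to a written retention step in one arm and to silence in the other. Staff who follow the text literally will ask intervention patients to stay in follow-up and may not ask usual-care patients. Collection of the 1-month and 3-month BSS scores would then depend partly on allocation, in a trial of at most 25 patients who know their arm.

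At stake is the comparability of the two arms at follow-up. Intention-to-treat analysis needs outcomes from patients whatever treatment they took. Likelihood-based estimation protects the comparison when missingness depends only on data already observed. It does not protect against patients who leave because of how they feel after their last recorded score. A rule that treats the arms differently adds a source of uneven missing data that could be avoided.

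**Working it through.** **1. Figures in the plan.** The plan gives no withdrawal rate, retention target or dropout allowance, so there is no figure to reproduce. Sample Size gives up to 25 patients. The allocation ratio is not stated. Assuming 1:1, 25/2 = 12.5 per arm, and one patient is 1/12.5 = 8% of an arm.

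**2. Can usual-care participation be divided?** Table 2 lists eight instruments taking 45 minutes in all, of which the BSS takes 10. Study Design says the instruments can be given by phone. VA utilization is abstracted from the medical record (Secondary Outcome, Patient Engagement; Protected Health Information). A usual-care patient could therefore decline the full battery and still agree to a BSS call or to record abstraction. The stopping section does not provide for asking.

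**3. Retention by arm under the text as written.** Let w_B and w_U be the shares asking to withdraw in the intervention and usual-care arms, and c the share of those asked who agree to continue. All three are assumptions. If no usual-care patient is asked:

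- intervention retention = 1 − w_B(1 − c)
- usual-care retention = 1 − w_U
- gap = w_U − w_B(1 − c)

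If both arms are asked and accept equally, the gap is (w_U − w_B)(1 − c).

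| w_U | w_B | c | Intervention | Usual care | Gap (points) | Patients (gap × 12.5) | Gap if both asked |
|---|---|---|---|---|---|---|---|
| 10% | 10% | 25% | 92.5% | 90% | +2.5 | +0.31 | 0 |
| 20% | 20% | 50% | 90% | 80% | +10 | +1.25 | 0 |
| 30% | 30% | 75% | 92.5% | 70% | +22.5 | +2.81 | 0 |
| 10% | 20% | 50% | 90% | 90% | 0 | 0 | −5 |
| 10% | 20% | 25% | 85% | 90% | −5 | −0.63 | −7.5 |
| 10% | 30% | 50% | 85% | 90% | −5 | −0.63 | −10 |
| 10% | 30% | 25% | 77.5% | 90% | −12.5 | −1.56 | −15 |

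With equal request rates, the rule alone creates the gap. If the intervention's extra contacts prompt more requests, the gap can vanish or reverse. In those rows a common question makes the gap more negative, but only because fewer usual-care outcomes are lost.

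**4. Effect on precision.** Take a 5-point between-arm difference, an assumed SD of 6, two-sided 5% and the normal approximation. Power = Φ(5 / (6√(1/n_B + 1/n_U)) − 1.96).

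- 20% asking in each arm, half of the intervention patients accepting: n_B = 11.25, n_U = 10, power 48%.
- Nobody accepting: n_B = n_U = 10, power 46%.

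The loss of precision is small. The issue is balance.

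**5. Illustration of a completer mean (assumed inputs).** Take 12 usual-care patients. If k leave and their unseen BSS is d points above that of the stayers, the observed mean is too low by d × k/12.

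- k = 1, d = 10: 10 × 1/12 = 0.83
- k = 2, d = 5: 5 × 2/12 = 0.83
- k = 2, d = 10: 10 × 2/12 = 1.67, which is 1.67/5 = 0.33 of the 5 points that Sample Size calls clinically meaningful

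If the leavers score lower than the stayers, the sign reverses. If one of the two leavers in the last case agrees to stay, the error falls to 10 × (2/12 − 1/11) = 0.76. If both decline, it stays at 1.67. These are errors in a raw mean, not in the planned mixed model, which recovers whatever part the baseline or 1-month scores predict.

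**The case against.** The strongest defence is that the asymmetry follows from the design. Only intervention patients have a study-delivered treatment that can be stopped while assessments go on. For usual-care patients the assessments are the whole of their study activity, so a request to withdraw is close to a request to stop assessments. This stands as the likely reason for the sentence. It does not settle the matter, because the trigger is the same request in both arms and usual-care follow-up can be reduced without ending it.

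A reader might infer that usual-care patients are lost without being asked, and that retention does differ by arm. The documents support neither. The section neither provides for asking a usual-care patient nor forbids it, and consent pages are not part of the text available for review. Other retention features are equal by arm: $100 per assessment (Subject Compensation), follow-up by phone, video or in person (Study Design), and review of retention by the monitoring committee (Data and Safety Monitoring Plan). No withdrawal figures exist, and the offer may only offset withdrawals caused by the intervention's own burden.

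Nor should the contrast be widened. Intervention patients are offered only the outcome assessments. Neither arm is offered a shortened assessment, and the text does not say for either arm whether record abstraction continues after withdrawal.

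**Conclusion.** The point holds in a limited form and is minor. The written effort to retain outcome data depends on arm, and no other section supplies a usual-care equivalent. Retention may therefore differ by arm, by an amount and in a direction that the plan does not allow anyone to state. The range of +22.5 to −12.5 percentage points comes from assumed request rates of 10% to 30% and acceptance rates of 25% to 75%, with 1:1 allocation and no usual-care patient asked.

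Any bias in the BSS comparison is limited to the part of the missing scores that observed scores do not predict. A reader might take the 1.67-point figure as the bias in the primary analysis. It is not: it describes a completer mean under invented inputs, with no loss in the other arm.

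A common question makes the effort equal and should lose fewer outcomes. It does not guarantee equal retention.

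**What to change.** Amend the section on reasons for stopping so that one data-collection rule covers both arms. Any patient who asks to withdraw is asked, in the same words:

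- whether they will complete the remaining 1-month and 3-month assessments, or at least the BSS by phone;
- whether abstraction of utilization from the medical record may continue.

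Their wishes are respected either way. Staff other than the blinded assessor should ask. Record the extent of withdrawal (study contacts, assessments, record abstraction) and report it by arm. The change concerns outcome collection only and leaves the reasons for stopping as they are.

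The cost is about one sentence of protocol text, matching consent wording if needed, and one extra question to a patient who wants to leave. It needs no added visits or staff.

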## **Research Protocol/Protocol Addendum Template**

---
